All recruitment will be done at each study site by the site-specific PI. As each study site is a referral site for patients with chronic pancreatitis who have PD stones, no advertising will be performed. All patients will be recruited based on screening done prior to regularly scheduled clinic or procedural visits.

12. Training Plan

The PIs will be responsible for training all study staff. The initial training meeting will occur at the 1st Investigators Meeting involving all PIs, co-investigators, and the study coordinator. The protocol will be

reviewed in its entirety and all standard procedures will be reviewed. Informed consent will also be reviewed during this session to ensure consistency across the study sites. All questions from the study staff will also be answered during this time. The protocol will then be reviewed at each site with the site-specific PIs and research assistants.

Quarterly conference calls involving all PIs, study coordinator and research assistants will be held once enrollment begins to ensure that any questions the study group has are answered. In addition, all potential protocol changes will be discussed during these calls. Should an emergent protocol change be needed, an emergent conference call will be held to discuss the change and once agreed upon, the changes will be submitted to the respective Institutional Review Boards.

References

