COMIRB 19-0402

PI: [name]

Version Date: December 6, 2023

SARC Approved 5/8/2019

***Per-oral Pancreatoscopy-guided Lithotripsy vs. Extracorporeal Shock Wave
Lithotripsy For Treating Symptomatic Main Pancreatic Duct Stones in Chronic
Pancreatitis: A Multicenter Randomized Clinical Trial***

Lead Site: University of Colorado

Version Date: December 6, 2023

Table of Contents

Table of Contents.....	2
Synopsis	3
List of Abbreviations	4
Study Protocol.....	5
Research Questions and Hypothesis	5
Basic Design of the Study	7
Sample and Methodology	7
Subject Inclusion and Exclusion Criteria	9
Inclusion Criteria:	9
Exclusion Criteria:	9
Study Steps	10
Screening/Baseline Evaluation	10
Consent	10
Randomization	10
Treatment Regimens	10
Outcome Determination	11
Standard of Care/Research Procedure.....	12
Subject and Study Stopping Criteria.....	12
Data Collection Tool	13
Data Analysis Plan	13
Data and safety monitoring plan.....	14
Definition of AEs, serious AEs, and unanticipated problems	14
Procedures for documentation of adverse events	15
Monitoring of Data	16
Feasibility/Recruitment Plan/Materials	16
Training Plan.....	16

Synopsis

Title	Per-oral Pancreatoscopy-guided Lithotripsy vs. Extracorporeal Shock Wave Lithotripsy in Chronic Pancreatitis: A Multicenter Randomized Clinical Trial
Investigative sites	University of Colorado The Ohio State University Baylor St. Luke's Medical Center Methodist Dallas Medical Center University of Minnesota University Health, San Antonio Indiana University Washington University School of Medicine
Hypothesis	The central hypothesis is that per-oral pancreatoscopy- guided lithotripsy is superior to extracorporeal shock wave lithotripsy in clearance of main pancreatic duct stones, thereby improving pain levels and quality of life in patients with chronic calcific pancreatitis.
Primary Objective	To demonstrate the superiority of per-oral pancreatoscopy over extracorporeal shock wave lithotripsy in clearance of main pancreatic duct stones in patients with chronic pancreatitis. Failure to remove any or all stones with the initial intervention will be an outcome recorded for the study.
Secondary Objective	To demonstrate the effect of stone clearance to reduce pain and opiate use and improve quality of life.
Timeline	Enrollment will be performed over a 24-month time period with follow-up performed at 1, 3, 6, 12, 18, and 24 months after ductal clearance.

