Following baseline assessments and identification of main PD stones, patients will be randomly assigned to receive either PPL or ESWL as the primary lithotripsy method to fracture PD stones. Both these procedures represent potential next steps in the algorithm of managing PD stones.³ If partial clearance (removal of some, but not all stones) of PD stones is achieved as determined by the performing endoscopist, subjects can receive repeated PPL or ESWL sessions (for a maximum of 4 sessions total as is commonly practiced before referral for alternative therapy) until complete removal of stones is achieved.⁵ Failure to remove any main PD stones will be considered a failure of the treatment. Additionally, failure to achieve complete clearance within a maximum of 4 sessions of either PPL or ESWL will be considered a treatment failure, even if partial clearance is achieved.

Cross-over and/or combination therapy will be allowed at the discretion of the endoscopist after treatment failure. As described in the statistical analysis, under the intention-to-treat (primary) analysis, should cross-over occur, the final outcome of complete stone clearance will be attributed to the initial therapy. Under the per-protocol (secondary) analysis, in the case of cross-over, the final outcome of complete stone clearance will be attributed to the combination of ESWL and PPL. Similarly, in terms of survey collection, should cross-over occur, the analysis of the survey results will be attributed to the

originally assigned intervention in the intention-to-treat (primary) analysis. In the per-protocol (secondary) analysis, the outcomes will be attributed to the combination of both interventions resulting in technical success.

Patients who are randomized and subsequently found to have an exclusion criteria identified will continue follow-up per study protocol.

Stone clearance will be determined by occlusion pancreatography showing the absence of main PD stones. Complete stone clearance will be defined as the absence of stones in the head or body of the main PD. Partial stone clearance will be defined as the removal of more than 50% but less than 100% of stone/stone fragments in the head or body of the main PD.

[figure not shown]
Recurrence will be defined as the presence of stones following confirmed clearance in the final pancreatogram. To be considered as recurring, the stone must require intraductal lithotripsy for removal.

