ESWL will start at the lowest power level and will gradually be increased until 25% of the shocks have been delivered to help create vascular constriction to minimize the risk of hematoma. The middle 50% of the shocks will be equally distributed between the 1st 25% of shocks and the final 25% of shocks at the top level of power. The final 1000 shocks should be administered at the highest power level number. The range of shocks delivered will be limited to 4000 to 6000 shocks. The rate of shocks will range from 70-90/minute.

A KUB (kidney-urether-bladder)-right posterior oblique X-ray will be done within 7 days after the ESWL session to determine the level of fragmentation of the stones. The goal will be to continue ESWL until stone fragments are felt to be \leq 3mm.

Non-lithotripsy panreatoscopy maneuvers will be permitted in the ESWL arm and not result in primary endpoint failure.

5.5 *Outcome Determination*

An occlusion panreatogram following extraction of stone fragments will be obtained after the endoscopist/urologist has determined treatment completion. All patients will receive an ERP at the completion or either PPL or ESWL, with an occlusion panreatogram performed to determine stone

clearance. An initial pancreatogram (or PD image from cross-sectional test – MRCP, MRI, CT scan, or EUS) with stone location and two representative final occlusion pancreatogram images will be uploaded to the REDCap database and will be reviewed by a blinded endoscopist to assess the level of stone clearance (complete or partial).

6. Standard of Care/Research Procedure

The current standard of care for the treatment of PD stones varies by region. In Europe, extracorporeal shock- wave lithotripsy (**ESWL**) is a primary method by which stones are fragmented. Once ESWL is performed, however, ERP is still performed to remove the stone fragments. In Europe, ESWL is frequently performed by gastroenterologists who can perform ERP as well.

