Statistical Analysis: Comparison of technical success rate, defined as the rate of complete clearance of PD stones, between PPL and ESWL will be performing using the chi-squared test or Fisher's exact test. Secondary outcomes including adverse event (both overall and serious adverse event) rates, procedure length, and number of procedures will be compared using a chi-square test or Fisher's exact test for categorical variables and the Student's t test will for continuous variables. A p value <0.05 will be considered significant. In the primary analysis, all results will be analyzed under an intention-to-treat protocol. A per-protocol (secondary) analysis will also be performed where the technical success will be attributed to the combination of modalities resulting in achieving the primary outcome should cross-over occur.

To identify predictors for technical success, a multivariable logistic regression will be performed incorporating variables that were associated ($p<0.2$) with technical success on univariate analysis.

In terms of secondary outcomes, change in PANQOLI scores, VAS scores, and opiate daily doses will be compared between subjects in the PPL group and ESWL group. Additional outcomes to be measured include stone recurrences and number of chronic pancreatitis-related hospitalizations during the follow-up period. Should cross- over occur, under the primary (intention-to-treat) analysis, the outcomes will be attributed to the initially randomized intervention. In the secondary (per-protocol) analysis, the outcomes will be attributed to the combination of treatments resulting in technical success. A subgroup analysis will also be performed on patients who achieved only partial stone clearance (thus considered a treatment

failure) in the above-mentioned outcomes. Comparisons will be made using a chi-squared test or Fisher's exact test for categorical variables and the Student's t test for continuous variables. Paired t tests will be performed to evaluate individual changes within each arm. A p value <0.05 will be considered significant.

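### The primary endpoint can be scored two ways: failure to clear within 4 sessions is a treatment failure, yet clearance after cross-over is credited to the first therapy

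*Combined protocol and SAP*

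**What the plan says.** Section 3 (Sample and Methodology) contains both rules.

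- Failure: "failure to achieve complete clearance within a maximum of 4 sessions of either PPL or ESWL will be considered a treatment failure", even where partial clearance was reached.
- Timing of a switch: "Cross-over and/or combination therapy will be allowed at the discretion of the endoscopist after treatment failure".
- Primary (intention-to-treat) analysis: "should cross-over occur, the final outcome of complete stone clearance will be attributed to the initial therapy".
- Secondary (per-protocol) analysis: "in the case of cross-over, the final outcome of complete stone clearance will be attributed to the combination of ESWL and PPL".

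Other sections bear on how a rescued patient is scored.

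- Section 9 defines technical success, the variable in the primary test, as complete clearance. Its per-protocol rule says "technical success will be attributed to the combination of modalities resulting in achieving the primary outcome should cross-over occur". It also labels patients with only partial clearance as treatment failures.
- Section 5.4 says that pancreatoscopy manoeuvres without lithotripsy "will be permitted in the ESWL arm and not result in primary endpoint failure".
- The Synopsis, under Primary Objective, says "Failure to remove any or all stones with the initial intervention will be an outcome recorded for the study". Section 9 plans no test of that outcome.
- Section 5.5 requires an ERP with occlusion pancreatogram when PPL or ESWL is complete. An initial image and two final images "will be uploaded to the REDCap database and will be reviewed by a blinded endoscopist to assess the level of stone clearance".
- Section 2 states the primary endpoint as complete clearance, with no session limit, time point or cross-over rule.

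**The concern.** Because cross-over is open only to patients who have already failed, every crossed-over patient is a treatment failure by the plan's own definition. The primary analysis rule then appears to turn that failure into a success for the first-assigned therapy if the other modality clears the duct.

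Final clearance by first-assigned strategy is a legitimate question. It is not the one asked by specific aim 1, which is whether PPL removes stones more effectively than ESWL, nor the one implied by the failure definition.

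If the choice is left open until data are seen, the same patients could give a significant or a non-significant primary result according to which sentence is followed. The halfway interim analysis (Section 10.3), at which the DSMB may recommend stopping for clear superiority, inherits the same ambiguity, as does the futility provision in Section 7.

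**Working it through.** **1. How the text scores a patient who fails ESWL and is then cleared by PPL**

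| Source | Score implied |
|---|---|
| Section 3, 4-session rule | failure |
| Section 3, intention-to-treat attribution | ESWL success |
| Section 9, per-protocol wording | success possible after cross-over |
| Section 9, partial clearance called treatment failure | failure, used as an outcome label |
| Section 5.4, exemption for non-lithotripsy manoeuvres only | failure, by implication |
| Synopsis, failure with the initial intervention | leans to failure |
| Section 2 endpoint; Section 5.5 final images | silent on before or after a switch |

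**2. The plan's own sample size**

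Inputs from Section 9: ESWL 70%, PPL 90%, two-sided alpha 0.05, power 80%. Pooled-variance formula with mean rate 0.80:

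n per arm = [1.960·√(2·0.80·0.20) + 0.842·√(0.70·0.30 + 0.90·0.10)]² / 0.20² = (1.109 + 0.461)² / 0.04 ≈ 61.6, so 62.

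This matches the stated 62 per arm (124 in total). Power is 80.3% at 62 per arm and 87.2% at 75 per arm. No term allows for clearance gained by cross-over.

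**3. Effect of crediting rescue**

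Let c be the share of failures that cross over, s the clearance rate of the second modality, and f = c·s. The credited rate is p + (1 − p)·f. With fE for ESWL failures and fP for PPL failures, the difference is

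(0.90 + 0.10·fP) − (0.70 + 0.30·fE) = 0.20 − 0.30·fE + 0.10·fP.

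It shrinks whenever fP < 3·fE, because the 70% arm has three times as many failures to rescue.

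The documents give no c or s, so the values below are assumptions. Full rescue uses the other modality's planning rate (0.90 for ESWL failures, 0.70 for PPL failures); half rescue uses 0.45 and 0.35.

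| Assumption | ESWL vs PPL | Power, 62/arm | Power, 75/arm | n/arm for 80% |
|---|---|---|---|---|
| No rescue credit | 70% vs 90% | 80.3% | 87.2% | 62 |
| c = 25%, half rescue | 73.4% vs 90.9% | 72.5% | 80.5% | 75 |
| c = 50%, half rescue | 76.8% vs 91.8% | 63.3% | 71.7% | 92 |
| c = 50%, full rescue | 83.5% vs 93.5% | 41.4% | 48.4% | 159 |

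Opposite case: fE = 0.2 and fP = 0.8 give 0.70 + 0.06 = 76% vs 0.90 + 0.08 = 98%, so the gap widens to 22 points.

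**4. One data set, two results (75 per arm)**

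- Cleared by the assigned modality: 53 vs 68, chi-square p = 0.002.
- If 10 of the 22 ESWL failures and 2 of the 7 PPL failures clear after cross-over: 63 vs 70, chi-square p = 0.07, Fisher p = 0.12.

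**5. Per-protocol denominators**

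The plan does not say how crossed-over patients enter the single-modality denominators. If they were removed, each rate would become p / [p + (1 − p)(1 − c)]: 75.7% vs 92.3% at c = 25%, and 82.4% vs 94.7% at c = 50%. Both arms would be inflated.

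**The case against.** The strongest reply is that the plan does state a rule. Sections 2 and 9 define the endpoint simply as complete clearance, and Section 3 says cross-over is handled by intention to treat. On this view, treatment failure is only the gate that permits a switch, and attribution to the initial therapy only means analysis by randomised arm. This does not remove the conflict. Section 9 uses treatment failure as an outcome label, not only as a gate. Intention to treat fixes the arm in which a patient is counted, not whether a rescued patient scores success or failure.

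Several limits do stand.

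- No section expressly equates treatment failure with primary endpoint failure; Section 5.4 only implies it. The study flowsheet (Figure 1) could not be seen.
- The power losses rest on assumed rates. In the mildest scenario shown, 75 per arm keeps 80.5% power if all 150 patients are analysed. The 41% figure assumes that patients who failed one modality clear with the other at its full planning rate.
- The worked example sits near the tipping point: with 2 PPL rescues, 9 ESWL rescues instead of 10 give chi-square p = 0.044; with 10 and 3, p = 0.034. Both scorings favour PPL, and only significance changes.
- The per-protocol inflation is conditional on a removal that no section states, and it concerns a secondary analysis.
- There is a further gap: a patient with no stones removed can fail before session 4, and the text does not say whether the cap counts sessions across modalities.

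**Conclusion.** The concern holds. The sole primary endpoint gives incompatible scores to the same patient, and the documents do not resolve it. That finding rests on the text and needs no assumption.

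The size of the effect does rest on assumptions about cross-over and rescue, and on the planning rates of 70% and 90% being rates without rescue, which the documents do not say. Across the range shown, power at 62 per arm falls from 80% to between 73% and 41%. Shrinkage of the difference is the likelier direction, since widening needs PPL failures to be rescued more than three times as often as ESWL failures. This must be fixed before analysis.

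**What to change.** - **Primary endpoint.** Define it once: complete clearance with the assigned modality within the plan's 4-session maximum, judged by the blinded image review already planned. Analyse all randomised patients in their assigned arm, and score clearance reached only after cross-over as non-success for that arm. This also settles early no-removal failures and the cross-modality session count.
- **Images.** For crossed-over patients, have the blinded reader score images from the ERP that Section 5.5 already requires at completion of PPL or ESWL, taken before the switch.
- **Rescue.** Report final clearance after any rescue as a secondary outcome by randomised arm. Add a sensitivity analysis that counts post-rescue clearance as success.
- **Data.** Record the reason for each cross-over and the clearance status before it.
- **Per-protocol.** Keep first-line failures as failures of their own modality, and state the denominators.
- **Text.** Reconcile Sections 3, 5.4, 5.5 and 9. If the sponsor prefers final clearance by assigned strategy as primary, the plan should say so and add a cross-over assumption to the sample size.

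The cost is wording in Sections 3, 5.5 and 9, two data fields and one more image upload per crossed-over patient. The clinical permission to cross over is untouched.

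There are two downsides. Reported clearance rates will be lower in both arms. The switch is also an unblinded, discretionary decision, so an early switch would create a failure. If 5% of would-be ESWL successes were switched early, the rates become 0.70 × 0.95 = 66.5% vs 90% (23.5 points). If 5% of would-be PPL successes were, they become 70% vs 0.90 × 0.95 = 85.5% (15.5 points). The recorded pre-switch status and the sensitivity analysis would show this.

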Randomization will be performed using a 1:1 ratio. The investigator will then inform the patient which lithotripsy therapy will be subsequently performed.

5.4 *Treatment Regimens*

Per oral pancreatoscopy-guided lithotripsy

Standard ERP will be performed to cannulate the PD, perform pancreatic sphincterotomy, and stricture

dilation as necessary. A panreatoscope (Spyglass Digital System, Boston Scientific, Marlborough, MA) will then be inserted through the duodenoscope into the PD. For PPL, electrical pulses will be delivered through an aqueous medium by EHL or LL with the probe tip in contact with or 1-2mm away from the stone.

For EHL, the Nortech bipolar biliary EHL probe (1.9 Fr, 0.66 mm) will be used and lithotripsy will start at medium power and can be increased to high power (maximum of 100 Joules). In terms of frequency, the maximum frequency allowed will be 30 pulses/second. There will be no limit to the number of EHL probes used during a session of lithotripsy, but the maximum time of lithotripsy allowed will be 1 hour.

For LL, Holmium laser will be utilized with energy ranging from 1 to 10.5 Joules, a frequency of 8-14 Hz and a power from 5-25W. LL fibers will include 200, 272, and 365 μ meter fibers. Similar to EHL, a maximum of 1 hour of intraductal lithotripsy will be allowed. Both forms of intraductal lithotripsy can be performed during the same treatment session.

EHL and/or LL will be continued until stone fragments are \leq 3 mm or a maximum of 1 hour of lithotripsy.

Extracorporeal shock wave lithotripsy

Stone localization will first be performed by obtaining high-quality plain films of the pancreatic area in left and right oblique positions using a two-dimensional radiologic targeting system.

Depending on the stone localization, ESWL will then be performed with the patient in either slight left or right lateral decubitus with shock waves entering the body from the ventral side. The shockwaves will be focused first on the most downstream located stone within the main duct and then on other calculi moving from the head towards the body. If a stent has been inserted during preceding ERP then this may also serve as a guide to target main pancreatic duct stones by ESWL.

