Power analysis: A large meta-analysis by Moole et al found a complete stone clearance rate of 70% in patients who received ESWL in conjunction with ERCP.¹⁴ In contrast, the largest studies examining pancreatoscopy-guided lithotripsy methods have found complete stone clearance rates ranging from 83-99%.^{6,17} Using a conservative stone clearance rate of 90% for pancreatoscopy- guided lithotripsy, a sample size calculation was performed using a two-sided test with 80% power and significance (α) of 0.05. This demonstrated the need for 124 subjects total, with 62 in each arm. Accounting for an expected dropout rate of 20%, the sample size needed would be a total of 150, or 75 subjects in each arm.

10. Data and safety monitoring plan

A Data and Safety Monitoring Board (DSMB) will be established to monitor the data and safety of this project. A DSMB will be appointed by the study team and will include at a minimum: A senior faculty member clinician with substantial research experience within the Division of Gastroenterology and Hepatology at the University of Colorado who is not involved in the study, and will serve as the group leader, a statistician, and a senior gastroenterologist from a non- participating academic institution. The DSMB will meet every six months. DSMB meetings will be only open to designated DSMB staff and other individuals who have been approved to have access to unblinded data. Any recommendations for alteration or termination for part or all of the trial shall be based on consideration of the accumulating data in the context of totality of evidence. Specific statistical monitoring guidelines for safety and efficacy concerning the primary and secondary endpoints will be developed in cooperation with the DSMB.

10.1 *Definition of AEs, serious AEs, and unanticipated problems*

AEs are defined as any undesired, harmful, or pathological change in a patient as indicated by signs, symptoms, or laboratory changes that occur in association with the use of the trial interventions, whether considered intervention-related or not. This definition includes intercurrent illness or injuries, exacerbation of existing conditions, psychological events, psychosocial events, and AEs as a result of the study intervention. All endoscopic AEs will be defined and classified as recommended by the American Society for Gastrointestinal Endoscopy (ASGE).²⁰

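### Per-protocol analysis: crediting cross-over outcomes to the ESWL–PPL combination makes the grouping depend on the endpoint, so single-technique clearance rates can drift upwards

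*Combined protocol and SAP*

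**What the plan says.** Section 3 (Sample and Methodology) sets the condition for changing technique: "Cross-over and/or combination therapy will be allowed at the discretion of the endoscopist after treatment failure". The same section defines treatment failure as removing no main duct stones, or not reaching complete clearance within four sessions, even where clearance is partial. No other route to cross-over is described.

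For the primary, intention-to-treat analysis, Section 3 credits the final clearance outcome to the initial therapy. For the secondary, per-protocol analysis it says that "in the case of cross-over, the final outcome of complete stone clearance will be attributed to the combination of ESWL and PPL". It applies a similar rule to the survey results.

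Section 9 (Data Analysis Plan) repeats the rule for technical success. For the other outcomes, which include PANQOL, VAS and opiate dose, it says: "In the secondary (per-protocol) analysis, the outcomes will be attributed to the combination of treatments resulting in technical success".

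Neither section defines the per-protocol population or gives a denominator for the ESWL, PPL or combination rates.

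**The concern.** A patient reaches the combination category by first failing the assigned technique. Membership of the single-technique groups therefore depends on the result that those groups are meant to compare. If a crossed-over patient's outcome moves to the combination and nothing stays behind, each single-technique group keeps all its successes but only those failures who did not cross over. The clearance rate then reflects how often endoscopists choose to cross failures over, as well as how well the technique works. That choice is made by a clinician who knows which technique was used. The only blinded role described is image review (Section 5.5).

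The arm with more failures has more to lose from its denominator. At equal cross-over shares the comparison is therefore pulled towards no difference.

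A second gap follows from the wording. Section 3's clearance sentence covers any cross-over, while its survey sentence and Section 9 speak of combinations that end in technical success. It is unclear where a patient who crosses over and never clears is counted.

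**Working it through.** **Inputs.** All are from Section 9 unless noted.
- ESWL clearance 70%: the cited meta-analysis "found a complete stone clearance rate of 70% in patients who received ESWL in conjunction with ERCP".
- PPL clearance 90%, the plan's assumed rate.
- A "two-sided test with 80% power and significance (α) of 0.05".
- Allocation 1:1 (Section 5.3).
- Share of failures who cross over, c: not given in the documents, so it is an assumption shown over its range.

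**The plan's own figure.** With the pooled-variance formula and no continuity correction, and a mean rate of 0.80:

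n per arm = [1.960 × √(2 × 0.80 × 0.20) + 0.842 × √(0.70 × 0.30 + 0.90 × 0.10)]² / 0.20² = (1.109 + 0.461)² / 0.04 ≈ 61.6, rounded up to 62.

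This matches the plan: "This demonstrated the need for 124 subjects total, with 62 in each arm". Power at 62 per arm is 80.3%. The design rates are therefore a sound starting point.

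**Reading A: every crossed-over patient leaves the arm.** With true clearance p, the per-protocol rate is

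p / [p + (1 − p)(1 − c)].

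For c = 50%: ESWL 0.70 / (0.70 + 0.30 × 0.50) = 0.70 / 0.85 = 82.4%; PPL 0.90 / (0.90 + 0.10 × 0.50) = 0.90 / 0.95 = 94.7%.

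With equal shares in both arms:

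| c | ESWL | PPL | Difference (points) | Power, starting from 62 per arm |
|---|---|---|---|---|
| 0% | 70.0% | 90.0% | 20.0 | 80% |
| 25% | 75.7% | 92.3% | 16.6 | 70% |
| 50% | 82.4% | 94.7% | 12.4 | 55% |
| 80% | 92.1% | 97.8% | 5.7 | 28% |
| 100% | 100% | 100% | 0 | – |

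The power column refers to the per-protocol comparison on its reduced denominators, not to the primary test. It is a normal approximation and is rough where few failures remain.

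**Unequal shares, Reading A.**
- 80% of ESWL failures and 20% of PPL failures cross over: 0.70 / 0.76 = 92.1% against 0.90 / 0.98 = 91.8%, so PPL is 0.3 points lower.
- 20% of ESWL failures and 80% of PPL failures: 0.70 / 0.94 = 74.5% against 0.90 / 0.92 = 97.8%, a difference of 23.4 points.

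**Reading B: only patients who clear after cross-over move.** The share of failures leaving is c times the clearance rate after cross-over. Assume that 80% cross over and three quarters of them clear, so 0.80 × 0.75 = 0.60 leave. ESWL is 0.70 / (0.70 + 0.30 × 0.40) = 0.70 / 0.82 = 85.4%. PPL is 0.90 / (0.90 + 0.10 × 0.40) = 0.90 / 0.94 = 95.7%. The difference is 10.4 points. The drift is smaller than the 5.7 points left under Reading A at the same c, but it has the same direction.

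**Reading C: crossed-over patients also stay in their own arm as failures.** The rates remain 70% and 90% at every c, and there is no drift.

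**The case against.** The strongest reply is that the plan never says crossed-over patients leave their arm. Section 9's sentence on technical success can be read as a rule for crediting successes, and Section 3 separately calls failure to clear within four sessions a treatment failure. Taken together, these could give Reading C. This stands to the extent that the loss from the denominator is an inference. It is still the natural reading, because Section 3 contrasts attribution to the combination with the intention-to-treat attribution to the initial therapy, and nothing says the patient is also kept as a failure.

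It is also fair that the analysis is secondary, and that the plan does not state that its purpose is to show each technique alone.

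The documents do not support four stronger conclusions that a reader might draw:
- *That the rule erases a true PPL advantage.* At equal shares this happens only if every failure crosses over; at 50% the gap is still 12.4 points. Unequal shares can remove or reverse the gap, but can also widen it.
- *That poor responders leave the arm for PANQOL, VAS and opiate outcomes.* Failure to clear is not the same as a poor response, and whether clearance improves these outcomes is what the second aim tests. Section 3 also schedules the questionnaires after complete stone removal.
- *That a patient who crosses over and never clears belongs to no group.* Section 3's clearance sentence can be read to include such a patient; the placement is unclear, not absent.
- *That ESWL access differs between arms within the trial.* Sections 1 and 6 describe US practice in general, while Section 10.1 says that these procedures would typically be part of management at the study sites.

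**Conclusion.** The concern holds for the secondary per-protocol analysis. As worded, its grouping depends on failure of the endpoint being compared, and its denominators are undefined. If crossed-over patients leave their arm, the design difference of 20 points becomes 12.4, 5.7 or 0 points at equal cross-over shares of 50%, 80% or 100%. If only those who clear leave, the drift is smaller and in the same direction. With unequal shares the difference can move either way.

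These sizes rest on the plan's design rates and on assumed cross-over shares, since the documents give none. The primary intention-to-treat test and the sample size do not rest on this rule. The point should be corrected, but it does not threaten the trial's main conclusion.

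**What to change.** Change the per-protocol wording in Sections 3 and 9 so that both say the same thing:
- Each crossed-over patient stays in the denominator of the first technique received and counts there as a failure to clear with that technique. This agrees with Section 3's definition of treatment failure, and it keeps the expected rates at 70% and 90% whatever the cross-over share.
- Clearance after ESWL plus PPL is reported as a separate descriptive rate. Its denominator is all crossed-over patients, including those who never clear.
- PANQOL, VAS and opiate data of crossed-over patients stay in the group of the first technique received, flagged for cross-over.

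The cost is a wording change in two sections. The present rule already requires cross-over patients to be identified, and the endoscopist's freedom to cross over is untouched. The downside is a less favourable single-technique clearance rate in a secondary table.
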